## 1. INTRODUCTION

This Statistical Analysis Plan (SAP) defines the analysis samples, specifies the analysis, and guides the interpretation of results from the [SYN120-CL03](#) or SYNAPSE clinical trial. The SAP supplements the clinical protocol. Readers are encouraged to refer to the clinical protocol for details on the rationale for the intervention, eligibility criteria, conduct of the trial, clinical assessments and the timing of their use in the trial, definitions and reporting of adverse events, data management conventions, and regulatory oversight and compliance procedures. The reader is referred to the Investigator's Brochure for additional details on physiochemistry and pre-clinical and clinical pharmacokinetics and safety of the investigational product, SYN120.

In case of discrepancies between the SAP and the clinical protocol concerning matters of analysis, the SAP is authoritative. On all other matters, the clinical protocol is authoritative.

## 2. STUDY DESIGN

### 2.1. Overview

This is a multicenter, double-blind, placebo-controlled, two-arm, parallel-group, phase 2a randomized controlled trial to evaluate the safety, tolerability, and preliminary efficacy of a 16-week course of 100 mg QD SYN120 in men or women with a diagnosis of Parkinson's disease dementia (PDD) who are taking a cholinesterase inhibitor. Trial participation includes a screening visit, randomization to SYN120 or placebo, 16 weeks of follow-up on study drug, and a final safety visit 2 weeks after last dose of study drug. The trial is registered at Clinicaltrials.gov as study NCT02258152 (see <https://clinicaltrials.gov/ct2/show/NCT02258152>). Participants may also separately consent to DNA testing for a pharmacogenetics substudy. The aims and planned analyses of the pharmacogenetics substudy are not described here.

### 2.2. Study Objectives

The primary efficacy objective of the [SYN120-CL03](#) trial is to assess the effect of a fixed dosage of SYN120 on cognition as determined by the Cognitive Drug Research Computerized Cognition Battery (CDR) Continuity of Attention measure in patients with PDD treated with a stable dose of a cholinesterase inhibitor. The key secondary efficacy objective is to assess the effects of SYN120 in this population on CDR Quality of Episodic Memory. Other secondary and exploratory efficacy objectives include the effects of SYN120 on: (a) global impressions of change, (b) other measures of cognition, (c) activities of daily living, (d) nighttime sleep and daytime sleepiness, (e) positive symptoms, and (f) behavioral functioning.

The safety objectives of the [SYN120-CL03](#) trial are to assess the safety and tolerability of a fixed dosage of SYN120 by assessing adverse events (AEs), vital signs (including orthostatic blood pressure measurements), laboratory assessments, electrocardiography (ECG), Unified Parkinson's Disease Rating Scale (UPDRS) Parts I through IV, changes in intensity of symptomatic therapy, and Columbia Suicide Severity Rating Scale (C-SSRS).

The pharmacokinetic objectives of the [SYN120-CL03](#) trial are to estimate population-level pharmacokinetic parameters for plasma levels of SYN120.

### **2.3. Study Population**

Individuals eligible for trial participation are men or women at least 50 years old who have received a diagnosis of probable PDD according to the Movement Disorder Society Task Force clinical diagnostic criteria for dementia associated with Parkinson's disease ([Emre et al. 2007](#)) and who are taking a cholinesterase inhibitor. Detailed inclusion and exclusion criteria are specified in the clinical protocol.

Participants will be recruited from a total of 20 clinical sites located through the US.

### **2.4. Participant Flow**

After providing informed consent and determining eligibility, approximately 80 participants will be randomized to receive SYN120 100 mg QD or placebo in a 1:1 ratio, stratified by clinical site. In the active arm, SYN120 is titrated as follows: 20 mg QD for the first 7 days, 50 mg QD for the next 7 days, and 100 mg QD for the remaining 14 weeks. Participants in the placebo arm receive a matching pseudo-titration of placebo. Participants who consent to participate in the pharmacogenetics substudy have a blood sample collected for DNA testing. Participants and caregivers return to the study site for evaluations at weeks 4, 8, and 16 and will be telephoned at weeks 2 and 12 to assess for AEs. Participants who discontinue study drug should remain on study following the normal schedule of assessments. Patients withdrawing consent will undergo an Early Termination Visit, ideally while still taking study drug. All participants are asked to return for a Safety Follow-up Visit approximately 2 weeks after their last dose administration. Detailed descriptions of study procedures and timing are specified in the clinical protocol.

### **2.5. Treatment Allocation**

At the baseline visit, eligible participants are randomly allocated in equal proportion to one of two treatment groups, SYN120 100 mg QD or placebo, according to a permuted-block randomization schedule with a block size of 4, stratified by site. The randomization schedule was prepared by computer program by the unblinded study statistician. Stratification by site is achieved by distributing to sites allotments of study drug kits that consist of a full block from the permuted-block schedule.

### **2.6. Allocation Concealment**

The randomization schedule is known only by the unblinded study statistician who generated the schedule and by the study drug distributor and the sponsor's quality control and bioanalytical staff and subcontractors as specified in the [SYN120-CL03](#) Study Randomization Specification. Concealment of the true treatment allocation of specific participants is achieved by use of anonymous subject identifiers to link participants with specific study drug kits and by use of matching active and placebo tablets and titration schedules. Members of the SYNAPSE Steering Committee, site investigators and other site staff, clinical coordination and data management staff, the blinded study statistician, the medical monitor, and all participants are blinded to participant treatment allocations. The Safety Data Monitor (SDM) and members of the SDM Advisory Group are provided treatment-specific information in order to monitor the trial but

such information is masked by use of coded values to identify the treatment groups. The SDM may request the true treatment identities.

## 2.7. Schedule of Assessments

Assessments	Study Period Study Week Visit Window	Screen- ing a	Base- line	16-Week Treatment Period (Double-blinded Dosing) (Days 1–112)						Safety Follow Up	Early Term.	Unsche- duled	
				0 ±3 days	2 ±3 days	4 ±3 days	8 ±3 days	12 ±3 days	16 ±3 days				
		V1	V2	V3	V4	V5	V6	V7	V8	V99	V98		
Onsite clinic visit	X	X		X	X			X	X	X	X		
Obtain patient and caregiver informed consent	X												
Demographics; medical history including neurological and PD/PDD history	X												
Concomitant medications including anti-dementia and anti-Parkinson meds	X b	X		X	X			X	X	X	X		
BP and pulse (supine and standing) c	XXX	X		X	X			X	X	X	X d		
Weight (include height at Screening)	X							X		X			
Physical and neurological examination	X	X d		X	X			X		X	X d		
MoCA	X							X		X			
Preliminary eligibility assessment by Investigator	X												
CDR Computerized Cognition Battery e	XX	X			X			X		X			
ADAS-cog e		X						X		X			
ADCS-CGIC e								X		X			
PDAQ (reported by caregiver)		X						X		X			
SCOPA-SLEEP		X						X		X			
SAPS-PD		X						X		X			
NPI (reported by caregiver)		X						X		X			
UPDRS Parts I–IV f		X		X	X			X		X	X		
Study drug accountability		X		X	X			X		X	X		
Recording of AEs	X	X	X	X	X	X	X	X	X	X	X		
C-SSRS	X	X		X	X			X	X	X	X d		
Dispense IMP to patient/caregiver and provide dosing instructions		X		X	X						X d		
FSH (♀ who are not surgically sterile and are postmenopausal, only)	X												
Urine hCG (♀ of childbearing potential, only) g	X	X		X	X			X		X	X d		
Hematology h , chemistry (including liver function) i	X	X		X	X			X		X	X d		
TSH, freeT3 and free T4	X												
Vitamin B12	X												
Urinalysis j	X	X		X	X			X		X	X d		
SYN120 blood sampling k		X		X l	X l			X		X l	X d,l		
12-lead electrocardiogram m	X	X n		X	X			X		X	X d		
Pharmacogenetic sample collection (optional)		X o		X p	X p			X p					

♀ = female; AEs, adverse events; ADAS-cog, Alzheimer's Disease Assessment Scale—cognitive subscale; ADCS-CGIC, Alzheimer's Disease Cooperative Study-Clinician's Global Impression of Change; BP, blood pressure; CDR, Cognitive Drug Research; C-SSRS, Columbia-Suicide Severity Risk Scale; ECG, electrocardiogram; FSH, follicle stimulating hormone; hCG, human chorionic gonadotropin; IMP, investigational medicinal product; MoCA, Montreal Cognitive Assessment; NPI, Neuropsychiatric Inventory; PD, Parkinson's disease; PDAQ-15, Penn Parkinson's Daily Activities Questionnaire-15; PDD, Parkinson's disease dementia; SAPS-PD, PD-adapted Scale for Assessment of Positive Symptoms; SCOPA-SLEEP, Scales for Outcomes in Parkinson's Disease-Sleep Scale; TSH, thyroid stimulating hormone; UPDRS, Unified Parkinson's Disease Rating Scale.

Footnotes:

- a Screening period may not exceed 6 weeks. Note: For screen failures, document demographics and reason for ineligibility in source documents and eCRF.
- b At Screening, obtain complete medication history including anti-dementia and anti-Parkinson medications (current and those received within the past year). Record the date and time of the most recent dose of each anti-dementia and anti-Parkinson medication taken prior to the Screening assessment.
- c BP and pulse are to be measured after at least 5 minutes supine rest and again after standing for 1 and 3 minutes.
- d Optional assessments that may be performed for evaluation of AEs, at the Investigator's discretion.
- e Perform all cognitive and dementia-related assessments while patient is in ON state. Complete two training sessions during the screening period, as close to the Baseline visit as possible.
- f UPDRS is to be measured in ON approximately 1 to 3 hours after patients have taken a scheduled dose of levodopa (preferably their morning dose of levodopa). Patients will be instructed to have already taken their normally scheduled dose of levodopa before arriving at the study site in order to have their UPDRS Part III evaluated in the ON state. UPDRS in the ON state will be measured at a time representative of the ON state in that patient, not in the patient's "best" ON.
- g For female patients of childbearing potential, perform a urine hCG pregnancy test and document method of contraception at Screening and verify continuation of contraceptive method at each visit.
- h Hematology: hemoglobin, hematocrit, red blood cell count, total and differential white blood cell, and platelet count.
- i Chemistry: aspartate aminotransferase (AST/SGOT), alanine aminotransferase (ALT/SGPT), gamma-glutamyl transpeptidase (GGT), alkaline phosphatase (ALP), lactate dehydrogenase (LDH), total bilirubin (conjugated and unconjugated), albumin, creatinine, urea/BUN, bicarbonate, uric acid, total protein, sodium, chloride, potassium, calcium, phosphate, glucose, cholesterol, and creatine phosphokinase (CK).
- j Urinalysis: specific gravity, pH, ketones, blood, protein, and glucose. If urine dipstick positive for leukocytes, protein or erythrocytes, microscopic evaluation will be performed.
- k Blood sample for determination of SYN120 plasma concentration (and screening for presence of SYN120 metabolites) to be obtained at Baseline (Day 1) prior to initiation of dosing, Visit 4 (Week 4), Visit 5 (Week 8), Visit 7 (Week 16), Early Termination (if applicable), and Unscheduled Visit (optional, as per footnote d). Record date and time of SYN120 sample collection.
- l For blood sample collections at Visit 4 (Week 4), Visit 5 (Week 8), Visit 7 (Week 16), and Early Termination or Unscheduled Visit (if applicable), record the date and time when the patient took the last dose of IMP.
- m Resting supine 12-lead ECGs will be collected after the patient has been in a supine, or if unable, semi-supine (no more than 45 degrees) position for a minimum of 5 minutes. ECGs should be collected at a time during study visit when the patient is not experiencing dyskinesia that would interfere with an adequate recording.
- n At Baseline, obtain triplicate 12-lead ECGs (3 serial readings performed several minutes apart).
- o At Baseline, for patients who give consent for optional pharmacogenetic substudy, collect single blood sample (approximately 10 mL) for pharmacogenetic assessment. (If this sample is not collected at Baseline, it will be collected at the next possible in-clinic visit, i.e., Visit 4, 5 or 7.) See [Section 7.13](#) of the clinical protocol.
- p For patients who give consent for optional pharmacogenetic substudy but sample not collected at Baseline (or during previous visit), collect single blood sample (approximately 10 mL) for pharmacogenetic assessment. See [Section 7.13](#) of the clinical protocol.

### 3. STATISTICAL METHODOLOGY

#### 3.1. General Considerations

##### 3.1.1. Statistical Software

All statistical analyses will be performed using SAS (SAS Institute, NC, USA) or R (R Foundation for Statistical Computing, Vienna, Austria).

##### 3.1.2. Summary Statistics

Data will be summarized with respect to disposition, demographics, pre-treatment characteristics, safety outcomes, tolerability, and efficacy outcomes. Summary statistics for

continuous variables will include the number of subjects, the mean, median, standard deviation, and range. For categorical data, summaries will include counts and percentages.

### **3.1.3. Precision**

Results will generally be reported to 3 significant figures. Percentages will generally be reported to 0.1 percentage points. P-values will be reported to two digits when greater than or equal to 0.10, to three digits when greater than or equal to 0.00095 and less than 0.10, and as <0.001 for all smaller values.

## **3.2. Study Endpoints**

### **3.2.1. Efficacy Endpoints**

The primary efficacy endpoint is the change from baseline to the week 16 visit in the CDR Continuity of Attention composite score captured in the ON state.

The key secondary efficacy endpoint is the change from baseline to the week 16 visit in the CDR Quality of Episodic Memory composite score captured in the ON state.

The other secondary efficacy endpoints are the change from baseline to the week 16 visit in the following measures:

- Alzheimer's Disease Cooperative Study-Clinician's Global Impression of Change (ADCS-CGIC),
- Alzheimer's Disease Assessment Scale-cognitive subscale (ADAS-cog) total score captured in the ON state by an evaluator blinded to the results of all cognitive assessments,
- CDR Power of Attention composite score captured in the ON state,
- CDR Speed of Memory Retrieval composite score captured in the ON state,
- PDAQ-15 total score (reported by caregiver),
- SCOPA-SLEEP nighttime sleep and daytime sleepiness scores,
- SAPS-PD total score,
- NPI total score, caregiver distress total score, and subscale total scores for delusions, hallucinations, agitation/aggression, dysphoria, anxiety, euphoria, apathy, disinhibition, irritability/lability, aberrant motor activity, night-time behavioral disturbances, and appetite and eating abnormalities (reported by caregiver), and
- MoCA total score.

Exploratory efficacy endpoints include the change from baseline to the week 8 visit in the CDR Continuity of Attention and Quality of Episodic Memory composite scores captured in the ON state and the change from baseline to week 8 and 16 visits in the CDR Quality of Working Memory, Cognitive Reaction Time, and Reaction Time Variability composite scores captured in the ON state, individual component tasks of the CDR, i.e., Immediate Word Recall (Words recalled, Errors), Simple Reaction Time (Median Reaction Time), Digit Vigilance (Mean Reaction Time, Accuracy, False Alarms), Choice Reaction Time (Median Reaction Time, Accuracy), Numeric Working Memory (Median Reaction Time), Spatial Working Memory

(Median Reaction Time, Sensitivity Index), Delayed Word Recall (Words recalled, Errors), Word Recognition (Median Reaction Time, Original Stimuli Accuracy, Novel Stimuli Accuracy), and Picture Recognition (Median Reaction Time, Original Stimuli Accuracy, Novel Stimuli Accuracy), and scores for individual tasks of the ADAS-cog.

### 3.2.2. Safety Endpoints

The following safety endpoints will be evaluated:

- Proportion of participants experiencing the following and event rates relative to time at risk of: (a) any treatment-emergent AE (TEAE), (b) any severe TEAE, (c) any serious TEAE, (d) any TEAE at least possibly related to study drug, (e) any TEAE leading to permanent study drug discontinuation or early termination from the trial, and (f) any TEAE resulting in death, summarized across all MedDRA terms
- Proportion of participants experiencing and number of unique events of all TEAEs classified by seriousness, severity, relatedness to study drug, action taken with study drug, and outcome, summarized across all MedDRA terms
- Proportion of participants experiencing and number of unique events of each type of TEAE and serious TEAE classified by MedDRA system organ class, high level term, and preferred term
- Proportion of participants experiencing treatment-emergent orthostatic hypotension
- Mean 16-week change from baseline in supine and standing SBP, supine and standing DBP, and differences from supine to standing SBP and DBP
- Mean 16-week change from baseline in weight
- Proportion of participants experiencing treatment-emergent clinically significant laboratory abnormalities classified by assay, whether the abnormality is below or above the normal range, and visit, with cross-classification of frequencies of abnormalities from baseline to each scheduled post-baseline visit at which safety labs are performed
- Mean 16-week change from baseline in laboratory assays
- Proportion of participants experiencing treatment-emergent clinically significant ECG abnormalities
- Mean 16-week change from baseline in ECG parameters
- Mean 16-week change from baseline in UPDRS Part I score, II score, III score, I through III total score, Part IV dyskinesia score, Part IV clinical fluctuations score, Part IV other complications score, and Part IV total score
- Mean 16-week change from baseline in levodopa daily dosage (LDD) and levodopa equivalent daily dosage (LEDD)
- Proportion of participants reporting any treatment-emergent suicidal ideation
- Maximum post-baseline suicidal ideation planning, frequency, duration, controllability, deterrents, and reasons

- Proportion of participants reporting any post-baseline suicidal behavior, actual attempts, non-suicidal self-injurious behavior, interrupted attempts, aborted attempts, preparatory acts or behaviors, or completed suicide
- Maximum post-baseline suicidal behavior lethality and potential lethality

Reported proportions will use as their denominator all participants in the Safety and Tolerability sample (see [Section 3.5](#) below).

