Statistical Analysis	
Primary Outcome Variable
 
The primary analysis will be performed on the mITT analysis set and will use a shared-baseline repeated measures ANOVA that includes fixed effects for visit and the interaction between treatment group and post-baseline visit, random center-specific intercepts, and unstructured within-person covariance.
 
Secondary and Exploratory Outcome Variables
 
Outcomes that are approximately normally distributed will be analyzed as described above for the primary outcome variable. Outcomes that are not normally distributed will be transformed or compared between the treatment groups using a van Elteren test that incorporates stratification by center. The key secondary outcome of CDR Quality of Episodic Memory will be tested for significance using the mITT analysis set at two-tailed alpha = 0.05. Other secondary outcomes will also be tested at two-tailed alpha = 0.05 using the mITT analysis set, recognizing that the totality of results will be evaluated in judging the potential of SYN120 as a therapeutic agent for PDD.
 
Safety Analysis
 
The assessment of safety will focus on the frequencies of individual AEs, vital signs (particularly orthostatic hypotension), UPDRS, abnormal laboratory test results, and ECG abnormalities, particularly treatment-emergent events. The frequency and type of any observed suicidal ideation will be described. The analyses will use the SS, Fisher's exact test for comparison of the proportion of participants in each treatment group experiencing a given AE or abnormal finding, and negative binomial regression for total counts of AEs.
 
Tolerability
 
Tolerance to SYN120 will be evaluated by recording the proportion of participants who discontinue IMP and by testing for a treatment-dependent difference in the time to discontinuation.

Table 1: Schedule of Events/Evaluations

Assessments	Study Visit	Study Period	Screening ^a	Baseline Predose	16-Week Treatment Period (Double-blinded Dosing) (Days 1-112)						Safety Follow Up (Post Dose Follow Up)	Early Term.	Unscheduled	
					0	2 (±3 days)	4 (±3 days)	8 (±3 days)	12 (±3 days)	16 (±3 days)	18 (± 3 days)			
					−6 to −1	V3 (phone call)	V4	V5	V6 (phone call)	V7	V8	V99	V98	
Onsite clinic visit			X	X		X	X			X	X	X		X
Obtain patient and caregiver informed consent			X											
Demographics; medical history including neurological and PD/PDD history			X											

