- ^b At Screening, obtain complete medication history including anti-dementia and anti-Parkinson medications (current and those received within the past year). Record the date and time of the most recent dose of each anti-dementia and anti-Parkinson medication taken prior to the Screening assessment.
- ^c BP and pulse are to be measured after at least 5 minutes supine rest and again after standing for 1 and 3 minutes. At Screening Visit three sets of readings are performed approximately 10 minutes apart. This is the only visit with 3 sets of BP readings.
- ^d Optional assessments that may be performed for evaluation of AEs, at the Investigator's discretion.
- ^e Perform all cognitive and dementia-related assessments while patient is in ON state. Complete two training sessions during the screening period, as close to the Baseline visit as possible.
- ^f UPDRS is to be measured in ON approximately 1 to 3 hours after patients have taken a scheduled dose of levodopa (preferably their morning dose of levodopa). Patients will be instructed to have already taken their normally scheduled dose of levodopa before arriving at the study site in order to have their UPDRS Part III evaluated in the ON state. UPDRS in the ON state will be measured at a time representative of the ON state in that patient, not in the patient's "best" ON.
- ^g For female patients of childbearing potential, perform a urine hCG pregnancy test and document method of contraception at Screening and verify continuation of contraceptive method at each visit.
- ^h Hematology: hemoglobin, hematocrit, red blood cell count, total and differential white blood cell, and platelet count.
- ⁱ Chemistry: aspartate aminotransferase (AST/SGOT), alanine aminotransferase (ALT/SGPT), gamma-glutamyl transpeptidase (GGT), alkaline phosphatase (ALP), lactate dehydrogenase (LDH), total bilirubin (conjugated and unconjugated), albumin, creatinine, urea/BUN, bicarbonate, uric acid, total protein, sodium, chloride, potassium, calcium, phosphate, glucose, cholesterol, and creatine phosphokinase (CK).
- ^j Urinalysis: specific gravity, pH, ketones, blood, protein, and glucose. If urine dipstick positive for leukocytes, protein or erythrocytes, microscopic evaluation will be performed.

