10.8 Determination of Sample Size

A total sample size of 80 or 40 in each group will provide at least 80% power to detect a true treatment difference equal to an effect size of 0.69 assuming up to 15% loss to follow up and using a two-tailed test at alpha = 0.05 based on a simple two-sample t-test. Additional power will be obtained from the proposed analysis using a shared-baseline repeated measures ANOVA.

Approximately 120 patients will be screened, assuming a 33% screen failure rate, to randomize 80 patients.

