### **3.9.5. Blood Pressure**

The absolute level and the absolute change from baseline of supine and standing SBP, supine and standing DBP, and differences from supine to standing SBP and DBP will be summarized as means, standard deviations, medians, and ranges at each visit by treatment group. The proportion of participants who experience orthostatic hypotension (as defined in [Section 3.3.11](#)) at the week 4, 8, and 16 visits and at any post-baseline visit will be summarized by treatment group.

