### **3.9.6. Additional Continuous Safety Outcomes**

The additional continuous safety outcomes of weight, ECG parameters, UPDRS scores (Part I score, Part II score, Part III score, Parts I through III total score, Part IV dyskinesia score, Part IV clinical fluctuations score, Part IV other complications score, and Part IV total score), LDD, and LEDD and their absolute change from baseline will be summarized as means, standard

deviations, medians, and ranges at each visit by treatment group. Treatment-dependent differences in 16-week change scores will be estimated in the ST sample for UPDRS scores using the shared-baseline, repeated-measures analysis of variance described for the primary efficacy analysis in [Section 3.8.1](#).

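### Blood pressure and ECG change endpoints get by-arm summaries with no between-arm estimate, although the SAP's baseline-adjusted model could supply one at little cost

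*SAP*

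**What the plan says.** The safety paragraph of the protocol synopsis sets the emphasis: "The assessment of safety will focus on the frequencies of individual AEs, vital signs (particularly orthostatic hypotension), UPDRS", followed by laboratory and ECG abnormalities. SAP 3.2.2 turns this into two kinds of endpoint.

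- **Continuous:** "Mean 16-week change from baseline in supine and standing SBP, supine and standing DBP, and differences from supine to standing SBP and DBP", and the 16-week mean change in ECG parameters. Protocol 10.2.4 includes QTcF among the ECG variables.
- **Binary:** the proportions with treatment-emergent orthostatic hypotension and with treatment-emergent clinically significant ECG abnormalities.

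For the continuous blood pressure measures, SAP 3.9.5 says that level and change "will be summarized as means, standard deviations, medians, and ranges at each visit by treatment group". It adds the proportion with orthostatic hypotension at Weeks 4, 8 and 16 and at any post-baseline visit. SAP 3.9.6 gives ECG parameters, weight and levodopa dosage the same descriptive treatment, then makes one exception: "Treatment-dependent differences in 16-week change scores will be estimated in the ST sample for UPDRS scores", using the model of SAP 3.8.1. That section credits the model with adjusting for chance baseline differences and with a possible efficiency gain when there are several follow-up visits and drop-out.

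**The concern.** Mean change in orthostatic pressure and in QTcF are named endpoints, but no section says how the arms are to be compared on them. The report will show two columns of means and SDs, and readers must form the difference and its uncertainty themselves. The difference they can form is the unadjusted change score. It makes no use of the regression of the Week 16 value on Baseline, and the Week 16 mean takes nothing from patients who were seen at Week 4 or 8 but not at Week 16.

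The SAP already specifies a model that does both and applies it to UPDRS. The assessment schedule collects blood pressure, ECG and UPDRS at the same on-treatment visits (Baseline, Weeks 4, 8 and 16), so nothing in data collection explains the different handling. With about 34 to 40 patients per arm, even a modest widening of the interval matters for a safety signal.

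**Working it through.** **The plan's own figure.** Protocol 10.8 sets "A total sample size of 80 or 40 in each group", for "at least 80% power to detect a true treatment difference equal to an effect size of 0.69", with up to 15% loss, "using a two-tailed test at alpha = 0.05 based on a simple two-sample t-test". This concerns the primary endpoint, but it fixes the numbers available.

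- Patients per arm with Week 16 data: 40 × 0.85 = 34.
- Noncentrality: 0.69 × √(34/2) = 2.845, with 66 degrees of freedom. Power is 80.05%, so the stated figure reproduces.
- In reverse, 34 / 0.85 = 40 per arm, 80 in total.

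No power or precision is stated for blood pressure or ECG change.

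**Assumed inputs.** The documents give neither the SD of these measures nor the correlation ρ between Baseline and Week 16. I take ρ from 0.3 to 0.9, with equal variance at both visits.

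**Formulas**, with n = 34 per arm:

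- SE of the raw change difference = SD × √(2(1−ρ)) × √(2/n)
- SE of the baseline-adjusted difference = SD × √(1−ρ²) × √(2/n)
- Ratio adjusted/raw = √((1+ρ)/2)

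| ρ | Ratio | SE reduction, baseline adjustment | SE reduction, repeated-measures model with 15% loss |
|---|---|---|---|
| 0.3 | 0.806 | 19% | 20% |
| 0.5 | 0.866 | 13% | 14% |
| 0.7 | 0.922 | 8% | 9% |
| 0.8 | 0.949 | 5% | 6% |
| 0.9 | 0.975 | 2.5% | 4% |

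The last column comes from the information matrix of the shared-baseline model with visits Baseline, 4, 8 and 16. It assumes 40 per arm, cumulative loss of 5%, 10% and 15%, equal correlation between all visits and known variances. The comparator is the raw change on 34 per arm.

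**In sample-size terms.** At ρ = 0.5 the adjusted analysis is worth 34 / 0.75 ≈ 45 patients per arm on the raw change score.

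**On the measurement scale.** With an assumed SD of 15 (mm Hg or msec), the 95% half-width is 1.96 × SE:

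- ρ = 0.3: 8.4 falls to 6.8
- ρ = 0.5: 7.1 falls to 6.2
- ρ = 0.7: 5.5 falls to 5.1

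**QTcF with a triplicate baseline.** Averaging three Baseline readings breaks the equal-variance assumption. Take an assumed correlation of 0.7 between visits and 0.85 within a visit.

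- Variance of the averaged baseline: (1 + 2 × 0.85)/3 = 0.90
- Adjusted residual variance: 1 − 0.7²/0.90 = 0.456
- Raw change variance: 1 + 0.90 − 2 × 0.7 = 0.50
- SE ratio: √(0.456/0.50) = 0.955, a gain of about 5% rather than 8%

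**Bias.** Simulated trials (400 for each ρ of 0.3, 0.5 and 0.7; 40 per arm; 12–19% loss depending on earlier readings) gave SE ratios of 0.83, 0.90 and 0.91. Neither method was materially biased.

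**The case against.** The strongest reply is that descriptive safety reporting is a declared choice. Protocol 10.5.1 plans descriptive summaries for vital signs and ECGs, the SAP follows it, and laboratory values, weight and levodopa dosage are handled the same way. UPDRS is the exception. In an 80-patient Phase 2a trial this is defensible, and it stands as a reason to treat the point as an improvement rather than an error.

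Several stronger readings are tempting, but the documents do not support them.

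- **That these measures get nothing but raw mean changes.** Both also have proportions in SAP 3.2.2, and 3.9.5 reports orthostatic hypotension by visit. The protocol names Fisher's exact test for proportions with abnormal findings. The SAP safety section does not repeat that test, and the SAP plans no between-arm difference or interval for these proportions either.
- **That the plan makes a noisy arm comparison.** It plans no comparison of these means at all. The gap is the missing estimate; lost precision is secondary.
- **That readers cannot judge the effect.** They can compute an unadjusted difference and interval from n, mean and SD.
- **That Week 4 and Week 8 readings are thrown away.** They are tabulated at their own visits and, for blood pressure, feed the any-visit proportion. Only the Week 16 mean gains nothing from them.
- **That Screening pressures are wasted.** Table 1, footnote c of the protocol says "At Screening Visit three sets of readings are performed approximately 10 minutes apart". Under protocol 10.3 these are the fallback baseline when the Baseline reading is missing.
- **That QTcF mean change is singled out as a headline endpoint.** The synopsis names ECG abnormalities. QTcF enters the change endpoint as one of the ECG parameters and is otherwise handled through thresholds.

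**Conclusion.** The point holds as a low-cost improvement. The SAP defines continuous change endpoints for blood pressure and ECG and plans no between-arm estimate or interval for them, while a suitable model is specified and used for one safety measure only. Baseline adjustment would cut the SE of the Week 16 difference by about 8% to 19% for correlations from 0.7 down to 0.3. At 0.8 or above the gain is about 6% or less, and for QTcF with an averaged baseline it may be smaller than the simple formula suggests. The correlations and the SD of 15 are assumptions. The claim concerns precision and completeness of reporting. It does not say that the planned summaries are biased or that the safety conclusions would be wrong.

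**What to change.** Extend the modelling sentence in SAP 3.9.6 to four further outcomes: supine-to-standing change in SBP, the same in DBP, standing SBP, and QTcF. Specify the following.

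- **Visits:** Baseline, Week 4, Week 8 and Week 16. The code in SAP 3.8.1 has three visit levels, so the contrasts need a fourth.
- **Sample and treatment variable:** the Safety and Tolerability sample by treatment actually received, as SAP 3.5 classifies it. The SAP 3.8.1 code uses the randomised-treatment variable (trtrnd), which must be replaced.
- **Orthostatic change:** the maximum supine-to-standing decrease over the 1- and 3-minute readings, matching SAP 3.3.11. State which standing reading is used for standing SBP.
- **QTcF baseline:** for this analysis, the average of the three Visit 2 readings, as protocol 4.3.1 and 7.16 define it. Say so explicitly, because protocol 10.3 otherwise points to the last non-missing pre-dose value.
- **Reporting:** arm differences with 95% confidence intervals at each post-baseline visit, labelled as estimation without formal testing.

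Keep the descriptive tables and the proportions. The Screening pressure sets need not enter the model. The cost is a few lines of SAP text and a few more fits of a model already specified, with no new data. The downside is some additional nominal intervals in the safety tables.
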